7.6 Follow-up of subjects withdrawn from treatment

Every attempt will be made to complete the primary follow-up in these patients.

7.7 Premature termination of the study

Planned interim analyses will be performed after 1, 2, 3, 4, 5, 6, 7, 8, 9, 10, 15, 20, 25, 50, and 100 inclusions. The interim analyses will only be directed at safety. The trial will be stopped because of any safety issue of the treatment under study, defined as a higher occurrence of SAEs in the treatment than in the control group. There will be no interim analysis for efficacy in this trial, since it is very unlikely that either 'futility' or 'proof beyond reasonable doubt' will be achieved prematurely in this relatively small phase 2 clinical trial.

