4.4 Sample size calculation

This is a phase 2 trial aiming at estimation of safety and potential of efficacy. Power calculations are hampered by lack of any data on ghrelin effects in patients with postanoxic encephalopathy. An intended sample size of 160 patients is based on analysis of any shift in the direction of a better outcome on the CPC scale, a mean CPC score without treatment at six months of 3.20, SD of 1.8 (based on our observations on natural history in 277 patients)⁷, a mean difference between treated and untreated patients of 0.8 points on the CPC scale, alpha of 0.05 and power of 80%. The mean difference of 0.8 points on the CPC scale may be an overestimation of potential benefit. The consequent relatively small sample size is considered justified, given the need for larger future phase 3 trials if potential benefit is demonstrated. Interim analyses will only be directed at safety (comparison of SAEs between treatment groups), so no additional subjects need to be included to compensate for interim analyses.

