8.2 AEs, SAEs and SUSARs

8.2.1 (Serious) Adverse events reporting

As this is a randomised controlled trial with a new drug all (serious) adverse events mentioned in paragraph 8.2.2 and 8.3.3 are required to be reported to the Sponsor and recorded in the electronic database. The sponsor is responsible to report the SAE to the accredited METC that approved the protocol.

Reporting of SAEs will be the responsibility of the study coordinator and the principle investigator. The local principle investigators will report on AEs, SAEs and SUSARs within the relevant time windows mentioned below. A dedicated study nurse will collect all AEs, SAEs, and SUSARs and discuss these with the principle investigator, every week.

Since case fatality in the patient population under study is known to be 50-60%, with most deaths occurring in the first week of ICU admission, line listing of all SAEs including deaths is requested, with reporting to the accredited METC once per two months. Exceptions will be made for (1) the first ten inclusions in the trial, (2) SAEs that are probably related to the trial, and (3) Suspected Unexpected Serious Adverse Reactions, for which expedited reporting will take place.

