8.2.4 Deaths

For SAEs with the outcome of death, the date and cause of death will be recorded on the appropriate case report form. Deaths that occur during the protocol that are more likely related to disease progression will be considered as an expected AE.

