Thereafter, the DSMB will perform safety analyses after 15, 20, 25, 50, and 100 inclusions. At that time, the DSMB will review data on SAEs, SUSARs, poor outcomes, and deaths per centre. This information will be sent to the DSMB at one week \pm 3 days after inclusion for the interim analyses at 15, 20, and 25 inclusions. For these interim analysis, the trial will only continue after a positive sign from the DSMB. For the interim analyses at 50 and 100 inclusions, the information will be sent after having reached the secondary outcome measure at three months. In addition, the DSMB will review general aspects of the trial, including patient recruitment, patient inclusion, and unexpected events. Because of the expected high proportion of patients with a poor outcome in the patient group under study, and the consequent overlap between safety endpoints and the primary endpoint, the evaluation of safety by the DSMB will be quantitative and qualitative. In addition, suspected unexpected serious adverse reactions (SUSARs) will be reported <48 hours to the METC.

The composition, tasks and responsibilities of the DSMB are described in K5: DSMB Charter.

The DSMB will advise to stop the trial at the following moments:

- A higher number of SAEs in the treatment than in the control group
- Any SUSARs
- Any other safety issues

The advice(s) of the DSMB will be sent to the Principle Investigator of the study and the METC. Should the Principle Investigator decide not to fully implement the advice of the DSMB, the Principle Investigator will send the advice to the reviewing METC, including a note to substantiate why (part of) the advice of the DSMB will not be followed.

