9.4 Interim analysis (if applicable)

Please also see chapter 7: safety Reporting / DSMB. The trial will be monitored by an independent DSMB. Details on the composition of the DSMB and rules on analysis and reporting are included in K5: "DSMB charter".

The trial will be stopped because of any safety issue of the treatment under study, defined as a higher occurrence of SAEs in the treatment than in the control group, any SUSAR, or any other safety concern. There will be no interim analysis for efficacy in this trial, since we consider it very unlikely that either 'futility' or 'proof beyond reasonable doubt' will be achieved prematurely in this relatively small phase 2 clinical trial.

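### The safety stopping trigger is any numerical SAE excess on ghrelin, with no margin: a harmless drug would meet it in roughly 58% to 86% of trials, depending on which looks count

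*Protocol*

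**What the plan says.** Section 7.7 sets the schedule: "Planned interim analyses will be performed after 1, 2, 3, 4, 5, 6, 7, 8, 9, 10, 15, 20, 25, 50, and 100 inclusions". It says the looks concern safety only and that the trial will be stopped for a safety issue, "defined as a higher occurrence of SAEs in the treatment than in the control group". Section 9.4 repeats the rule with two further grounds: "defined as a higher occurrence of SAEs in the treatment than in the control group, any SUSAR, or any other safety concern".

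Section 8.5 (DSMB) is softer. The first ten looks are made patient by patient and are mainly qualitative. The later looks combine quantitative and qualitative evaluation. The DSMB gives advice, which the principal investigator may decline with a reasoned note to the METC. Its first listed ground for advising a stop is still the bare comparison: "A higher number of SAEs in the treatment than in the control group".

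Sections 8.2.2 and 8.2.3 list death as an SAE. Section 8.2.1 states that "case fatality in the patient population under study is known to be 50-60%, with most deaths occurring in the first week" of ICU admission. Section 8.2.4 adds: "Deaths that occur during the protocol that are more likely related to disease progression will be considered as an expected AE".

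Section 4.4 derives 160 patients with "alpha of 0.05 and power of 80" per cent. Because the looks are for safety only, it concludes, "so no additional subjects need to be included to compensate for interim analyses".

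Sections 8.5 and 9.4 refer to the DSMB charter (K5) for rules on analysis and reporting. The charter is not among the documents at hand.

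**The concern.** The trigger has no margin, significance level, probability threshold or minimum number of patients. One extra event on ghrelin satisfies it. With SAEs in at least half of the patients and repeated looks, one arm will usually be ahead at some point by chance alone.

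If the rule is followed, an inert or even a beneficial drug may be stopped on noise, and the trial may not deliver the power for which it was sized. If the DSMB sets the rule aside and uses judgement, as 8.5 allows, then 7.7 and 9.4 misstate how the trial is run. This is not a detail left for a later document: the protocol itself states the trigger three times.

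**Working it through.** **1. The plan's own figure.** Inputs from 4.4: difference 0.8, SD 1.8, alpha 0.05, power 80%.

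n per arm = 2 × (1.960 + 0.842)² × 1.8² / 0.8² = 2 × 7.85 × 5.0625 = 79.5, so 80 per arm and 160 in total. Power at 80 per arm is 80.3%. A one-sided test would need only 63 per arm, so the calculation is two-sided. The figure reproduces for a design that always completes.

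**2. Why a bare inequality triggers so often.** At one look with equal arms and no true difference, P(excess on ghrelin) = (1 − P(tie)) / 2, a little under one half. For the looks at 50 and 100 the differences have correlation √(50/100) = 0.707. Ignoring ties, P(excess at one or both) = 1 − [1/4 + arcsin(0.707)/(2π)] = 1 − (0.25 + 0.125) = 62.5%. Ties lower this to the simulated 57-60%.

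On the literal schedule, the trial stops at patient 1 if that patient is on ghrelin and has an SAE. At an assumed 40% risk this is 0.5 × 0.40 = 20%, at a point where no comparison group exists.

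**3. Simulation of the trigger.** Inputs:
- Looks from 7.7. Data timing from 8.5: about one week after inclusion up to 25 patients, and after the three-month outcome for 50 and 100.
- 1:1 allocation in blocks of 10, stratified by site (7.2). The number of sites is assumed: one stream or five sites.
- SAEs taken as deaths only. Assumed risk 40% by day 7 and 50% by three months, guided by the 50-60% in 8.2.1.
- Planning effect: assumed control CPC distribution (0.33, 0.14, 0.02, 0.01, 0.50), mean 3.21. A common odds ratio of 2.31 shifts it to (0.53, 0.14, 0.02, 0.01, 0.30), mean 2.41, a difference of 0.80. Deaths fall from 50% to 30%.
- Success means the trial was not stopped and the final Mann-Whitney test has two-sided p < 0.05.

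| Looks compared numerically | Harmless drug meets trigger | Planning effect: meets trigger | Planning effect: completes and significant |
|---|---|---|---|
| None | 0% | 0% | about 80% |
| 50 and 100 | 57-61% | about 6% | not run |
| 15, 20, 25, 50, 100 | 73-78% | 27-29% | about 60% |
| All 15 | 84-87% | 49-51% | about 43% |

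**4. Sensitivity.**
- With one constant SAE risk of 50-60% in both arms, a harmless drug meets the trigger in 57-58% (50 and 100), 72-74% (five looks) and 84-88% (15 looks). Over risks of 20-80% the 15-look figure is 77-91%.
- A second assumed CPC distribution (mean 3.19, SD 1.79, CPC 5 falling from 46% to 27%), with deaths only, gives a chance of completing with significance of 57-65% (five looks) and 41-44% (15 looks).
- Adding non-fatal SAEs unaffected by treatment (20-30% of patients, with 60-80% of deaths counted) gives 40-52% and 24-31%.

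**5. With a threshold.** Requiring z > 1.96 (one-sided nominal 0.025) at the five later looks stops a harmless drug in about 8% of trials and keeps power at 78-79%.

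**The case against.** The strongest reply is that the protocol does not intend a mechanical rule. Section 8.5 makes the first ten looks mainly qualitative and lets the investigator decline the DSMB's advice. It asks for qualitative judgement precisely because safety events overlap the primary endpoint. In one run of the literal rule, looks 1-10 accounted for about 64 of 87 percentage points of stopping under no effect. This stands. A reader might infer that the trial must stop at any of 15 looks, with 86% as the plain result. Section 8.5 does not support that, so 86% belongs only to the literal reading of 7.7.

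Other tempting readings also go too far:
- **That no operative safety boundary exists.** The charter is not shown, so this cannot be asserted.
- **That the sample size is wrong, or that the looks inflate the type I error.** Neither holds. The 160 reproduces, and safety-only looks leave the efficacy error rate uninflated, so the remark in 4.4 is right on that point. What it leaves out is the effect on power and completion.
- **That power is 43%.** This is not a figure from the protocol. It needs an assumed CPC distribution and an assumed link between CPC and SAEs.
- **That 8.2.4 removes disease-related deaths from the SAE count.** That section speaks of SAEs with fatal outcome, so its wording can be read as an expectedness label. It needs only a clarification.
- **That comparing counts rather than proportions is a major fault.** At 55% risk and 15 looks, the false-trigger rate is 86.5% on counts and 84.5% on proportions.

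None of this rescues the inequality. Section 8.5 itself keeps a bare excess as a ground for advising a stop, and under every reading tried at the stated 50-60% risk a harmless drug meets it more often than not.

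**Conclusion.** The concern holds as a badly fixed rule and an internal contradiction. Sections 7.7 and 9.4 state a mandatory stop, and 8.5 states advice and judgement. All three rest on a numerical excess without a margin.

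The reading that best fits 8.5, with numerical comparison from 15 inclusions onward, gives about 75% false triggering and about a 60% chance of completing with a significant result under the planning effect. The literal reading of 7.7 gives about 86% and 43%. Comparing only at 50 and 100 gives about 58% false triggering.

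The false-trigger figures depend little on the assumed SAE rate. The power figures depend heavily on the assumed CPC distribution and SAE composition, and should be quoted with their range of about 24-65%. All of them assume that the trigger, once met, ends the trial. To the extent that advice is declined, the loss is smaller.

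**What to change.** 1. Reconcile 7.7 and 9.4 with 8.5 and with the DSMB charter, so that all say whether the trigger is binding or advisory.
2. State that the first ten looks are case review without a numerical comparison between arms.
3. For the looks at 15, 20, 25, 50 and 100, replace the bare inequality with a pre-stated advisory statistical threshold. Apply it to the proportion of patients with an SAE and, separately, to all-cause death. The level should be agreed with the DSMB and METC; a one-sided nominal 0.025 is one example (step 5 of the working).
4. Make clear in 8.2.4 that deaths labelled as expected still count in this comparison.
5. In 4.4, report the operating characteristics of the chosen rule: false stops, power, and the chance of stopping under real harm.

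The cost is wording in the protocol and, where needed, the charter. The sample size does not change. The price is sensitivity, because a small real excess no longer triggers the rule automatically. In simulation, a 0.975 posterior-probability threshold (about 8% false stops) is crossed in about 43%, 61% and 79% of trials if mortality on ghrelin is 65%, 70% or 75% against 50%. At 0.95 the figures are about 55%, 73% and 89%, with about 15% false stops. The choice between such levels is for the DSMB and METC, and DSMB judgement remains essential under either.

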8. SAFETY REPORTING

8.1 Temporary halt for reasons of subject safety

In accordance to section 10, subsection 4, of the WMO, the sponsor will suspend the study if there is sufficient ground that continuation of the study will jeopardise subject health or safety. The sponsor will notify the accredited METC without undue delay of a temporary halt including the reason for such an action. The study will be suspended pending a further positive decision by the accredited METC. The investigator will take care that all subjects are kept informed.

8.2 AEs, SAEs and SUSARs

8.2.1 (Serious) Adverse events reporting

As this is a randomised controlled trial with a new drug all (serious) adverse events mentioned in paragraph 8.2.2 and 8.3.3 are required to be reported to the Sponsor and recorded in the electronic database. The sponsor is responsible to report the SAE to the accredited METC that approved the protocol.

Reporting of SAEs will be the responsibility of the study coordinator and the principle investigator. The local principle investigators will report on AEs, SAEs and SUSARs within the relevant time windows mentioned below. A dedicated study nurse will collect all AEs, SAEs, and SUSARs and discuss these with the principle investigator, every week.

Since case fatality in the patient population under study is known to be 50-60%, with most deaths occurring in the first week of ICU admission, line listing of all SAEs including deaths is requested, with reporting to the accredited METC once per two months. Exceptions will be made for (1) the first ten inclusions in the trial, (2) SAEs that are probably related to the trial, and (3) Suspected Unexpected Serious Adverse Reactions, for which expedited reporting will take place.

8.2.2 Adverse events (AEs)

Adverse events are defined as any undesirable experience occurring to a subject during the study, whether or not considered related to the use of Ghrelin. All adverse events reported spontaneously by the subject or observed by the investigator or his staff will be recorded. An adverse event should be reported within 10 working days to the Principle Investigator. A serious adverse event should be reported to the Principle Investigator within 24 hours of first knowledge. The following adverse events will always be reported:

- Flushing and stomach problems (mild anticipated adverse events);¹⁷
- Second cardiac arrest needing cardiopulmonary resuscitation (SAE);
- Death (SAE).

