Ghrelin is a naturally occurring hormone and mildly excitatory neurotransmitter. The presumed mechanism of action is slowing down of apoptosis.¹²⁻¹⁵ Since hypoxia induced neuronal inactivity was independently associated with progression towards irreversible damage, both *in vitro*¹⁶ and in patients,^{6,7} we assume that the beneficial effects of ghrelin are mediated by mild neuronal activation, preventing ill-fated neuronal inactivity.⁵ This is perpendicular to the classical view of neuroprotection by inhibition, which is currently applied in all comatose patients after cardiac arrest.

Ghrelin seems safe

Ghrelin has been administered as an infusion or a bolus in a variety of doses to at least 1850 study participants, including healthy participants and patients with obesity, prior gastrectomy, cancer, pituitary disease, diabetes mellitus, eating disorders, cardiovascular disease and neurodegenerative disease (for reviews please see^{17,18}). Taken together: there is strong evidence that ghrelin stimulates appetite and increases circulating GH, ACTH, cortisol, prolactin, and glucose in various patient populations. There is a paucity of evidence regarding the effects of ghrelin on LH, FSH, TSH, insulin, lipolysis, body composition, cardiac function, pulmonary function, the vasculature, and sleep (review¹⁷).

At the doses evaluated in the 66 published studies with adverse event reporting, ghrelin demonstrated an excellent short-term safety profile with few adverse effects.¹⁷ Serious adverse events such as pneumonia, enteritis, and lung cancer were extremely rare and difficult to attribute biologically to ghrelin administration. Most of the severe adverse events derived from 1 study of ghrelin v.s placebo administration in severely ill patients with pulmonary cachexia, a group that is vulnerable to developing additional medical problems.¹⁹ Mild adverse events occurred in approximately 20% of participants receiving ghrelin. The most common effect was transient flushing, which occurred in 10% of volunteers, but resulted in discontinuation of study medication in only 3 of the 939 participants in whom adverse event collection was reported.²⁰⁻²² There was no difference in the percentage of participants experiencing flushing between bolus and infusion routes of administration.

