7.1.3 Other study parameters

We assume that potential effects of ghrelin are mediated by mild neuronal activation, preventing ill-fated neuronal inactivity. This is based on studies under experimental in vitro and in vivo conditions.^{10,18} To study effects of ghrelin on neuronal activity, we consider brain activity as measured by the EEG. Continuous EEG measurements during day 0-3 after

cardiac arrest are performed in all participating hospitals in the context of current care. The following EEG measures will be extracted and studied in relation to ghrelin treatment: the temporal brain symmetry index (tBSI),²⁴ the cerebral recovery index (CRI)²⁵ and EEG background continuity.²⁶ All three measures strongly represent restoration of brain activity after an hypoxic insult and are strongly related to clinical recovery.

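### Seizures are neither a solicited adverse event nor an extracted EEG measure in a trial of neuronal activation; adding them would be a cheap improvement

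*Protocol*

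**What the plan says.** **Mechanism.** Section 1 of the protocol states that "Ghrelin is a naturally occurring hormone and mildly excitatory neurotransmitter". Section 7.1.3 adds: "We assume that potential effects of ghrelin are mediated by mild neuronal activation, preventing ill-fated neuronal inactivity". Section 6.3 says that ghrelin has not yet been given to comatose patients after cardiac arrest. Section 2 puts safety in the primary objective.

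**Solicited events.** In 8.2.2 the words "The following adverse events will always be reported" precede three items: flushing and stomach problems, a second cardiac arrest needing resuscitation, and death. The same section has a general rule: "All adverse events reported spontaneously by the subject or observed by the investigator or his staff will be recorded". In 8.2.1, "A dedicated study nurse will collect all AEs, SAEs, and SUSARs", with a weekly discussion.

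**EEG.** Under 7.1.3, continuous EEG is part of current care on days 0-3 in all participating hospitals. The measures to be extracted are the temporal brain symmetry index, the cerebral recovery index and background continuity. The protocol says of them: "All three measures strongly represent restoration of brain activity after an hypoxic insult and are strongly related to clinical recovery".

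**DSMB.** Under 8.5, the DSMB receives AEs as well as SAEs, SUSARs, poor outcomes and deaths for each of the first ten inclusions. For the reviews at 15, 20, 25, 50 and 100 inclusions, the listed data are SAEs, SUSARs, poor outcomes and deaths, with a general review that includes unexpected events.

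**The concern.** The EEG is used to look for the intended effect of neuronal activation, but not for a plausible unwanted effect of the same mechanism. Clinical seizures, electrographic seizures and status epilepticus are absent from the endpoints (7.1), the safety reporting (section 8) and the risk analysis (section 12). The nearest mention is synchronized periodic activity in 9.2, which serves only to define a subgroup by the 24-hour EEG.

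The protocol treats cardiovascular risk differently. Section 12.1.g names it as a vulnerability of this population, and 7.1.2 pre-specifies arrhythmia, blood pressure, heart rate and vasoactive drug doses.

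Without a prompt or a definition, the seizure count depends on what staff notice and choose to enter. Comatose patients cannot report events themselves. A moderate excess on ghrelin could be under-counted, and part of it might lie in EEG recordings that the trial reads only for recovery.

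**Working it through.** **1. Is there a solicited seizure item?** Setting the places side by side:

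| Place in the protocol | What it collects | Seizure item |
|---|---|---|
| 7.1.1 and 7.1.2, outcomes | CPC, fatality, awakening, cognition, cardiovascular, biomarkers, gastric volume | none |
| 7.1.3, EEG | three recovery measures | none |
| 8.2.2, always-reported list | flushing and stomach problems, second arrest, death | none |
| 8.2.2, general rule | any AE reported or observed | only if noticed and entered |
| 8.2.3, SAE criteria | serious events | only if serious |
| 8.5, first ten inclusions | AEs, SAEs, SUSARs, poor outcomes, deaths | if entered as an AE |
| 8.5, inclusions 15 to 100 | SAEs, SUSARs, poor outcomes, deaths, unexpected events | if an SAE, or if raised as unexpected |

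The scope of reporting is blurred further in 8.2.1, which requires the events named in 8.2.2 and 8.3.3. There is no section 8.3.3.

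**2. Observation windows.** The procedures table in 7.3 places treatment on days 0-6, which is 7 days. EEG runs on days 0-3, which is 4 days. Routine EEG can therefore supply electrographic events for 4 of the 7 treatment days.

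**3. The plan's own sample size.** Inputs from 4.4: difference 0.8, SD 1.8, alpha 0.05 (taken as two-sided), power 80%.

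n per arm = 2 × (1.960 + 0.842)² × (1.8/0.8)² = 2 × 7.85 × 5.0625 = 79.5, rounded up to 80. The total is 160, as stated.

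**4. What 80 per arm could show for seizures.** The protocol gives no seizure rate, so all rates here are assumptions. For two proportions with pooled variance under the null and p̄ = (p₁ + p₂)/2:

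power = Φ{ [ |p₂ − p₁| √n − 1.96 √(2p̄(1 − p̄)) ] / √(p₁(1 − p₁) + p₂(1 − p₂)) }

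For 10% vs 20%: (0.10 × 8.944 − 1.96 × 0.505) / 0.500 = −0.19, and Φ(−0.19) = 42%.

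| Placebo vs ghrelin (assumed) | Power | Half-width of 95% CI for the difference |
|---|---|---|
| 5% vs 10% | 22% | 8 points |
| 10% vs 20% | 42% | 11 points |
| 20% vs 30% | 31% | 13 points |
| 20% vs 40% | 79% | 14 points |

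The half-width is 1.96 √{[p₁(1 − p₁) + p₂(1 − p₂)]/80}; for 10% vs 20% it is 1.96 × √(0.25/80) = 0.110.

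**5. Cost of incomplete recording.** Suppose the true rates are 20% vs 40% and the same fraction of events is recorded in both arms:
- All recorded: 20% vs 40%, power 79%.
- 75% recorded: 15% vs 30%, power 62%.
- 50% recorded: 10% vs 20%, power 42%.

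**The case against.** The strongest case against is that the list in 8.2.2 is a minimum and not the scope of collection. Every observed AE is recorded, a nurse collects them all, and a seizure meeting the criteria in 8.2.3 is reported as an SAE. The DSMB includes a neurologist, sees AEs and patient files for the first ten inclusions, and may later raise unexpected events or any other safety issue. The eCRF and the DSMB charter, which are not shown, may add detail. All of this stands: seizures are not excluded from capture. What is missing is a uniform definition, a prompt, and a stated route to the DSMB for non-serious events after inclusion ten.

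A reader might infer two stronger claims, and the protocol supports neither.

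- *That seizures are the harm most to be expected.* The protocol calls ghrelin mildly excitatory but never names seizures as a risk. The neurocognitive effects it reports are somnolence, fatigue, vertigo and mood change, and the vulnerability it names is cardiovascular. Seizures are a plausible harm by inference from the mechanism, and no more than that.
- *That without systematic recording no valid comparison is possible.* The trial is double blind, the treating intensive care physician stays blinded, allocation is 1:1 stratified by site, and EEG is current care in all hospitals. Nothing in the protocol suggests that recording would differ by arm. Equal under-recording dilutes the difference and costs power; it does not invalidate the comparison.

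**Conclusion.** The point holds as a cheap improvement, not as an error in the plan. Seizures are neither solicited in 8.2.2 nor extracted in 7.1.3, and non-serious ones have no clear route to the DSMB after the first ten inclusions.

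The size of the gain is uncertain. If true rates were 20% vs 40%, full recording instead of half would raise power from 42% to 79%. If they were 5% vs 10%, power would be only 22% even with full recording. These figures rest on assumed rates, on 80 evaluable patients per arm, and on equal recording in both arms. The benefit is a defined count by arm with an honest interval; it is not a well-powered test. The sample size does not change.

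**What to change.** 1. In 8.2.2, add clinical seizure, electrographic seizure and status epilepticus to the always-reported list, each with one definition for all centres. Record clinical events over the whole treatment week (days 0-6). Take electrographic events from the routine EEG on days 0-3.
2. In 7.1.3, add these items as an EEG safety measure, compared by arm with a 95% confidence interval.
3. In 8.5, include them in every DSMB report, whether or not the event was classed as an SAE.
4. In 8.2.1, correct the reference to 8.3.3.

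The cost is a few eCRF fields and an agreed definition, because the EEG is already recorded in current care. Two limits should be stated openly: there will be no electrographic data after day 3, and power is low unless the excess is large. Nothing in treatment or sample size changes.
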